#### 6.1.2 Procedure for On-study and Treatment Deviations

Any amendments to the study protocol need to be approved by the institutional review board (IRB) at both the study sponsor site as well as at all participating centers. All deviations or single subject exceptions to the study protocol must be reported to the primary IRB of the participating site, and to [name].

### 6.2 Informed Consent

The investigational nature and objectives of the trial, procedures and treatments involved, attendant risks and discomforts, and potential alternative therapies will be carefully explained to the subject and a signed informed consent will be obtained. Documentation of informed consent for screening will be maintained in the subject's research chart and medical record.

The participating clinicians who are approved at City of Hope must obtain informed consent and confirm in the electronic medical record that the patient has received the Notice of Privacy

Practice. This must be obtained before confirming eligibility, registration and the subject receiving any study treatment.

##### 6.3.1 Slot verification and reservation

As the study nears completion of accrual, study team personnel (including physicians, protocol nurses and/or CRCs) may wish to contact the DCC to verify slot availability and to reserve an open slot or be placed in queue for slot opening. Slots may only be held for a limited time which will be determined by the PMT. The Data Coordinating Center should be notified of cancellations of prospective participants holding slots as soon as possible.

##### 6.3.2 Registration procedure

To register a participant, the subsequent procedure is to be followed.

1. City of Hope staff or the participating institution's data manager/coordinator/research nurse should contact the DCC via telephone or email to provide notification regarding the pending registration and communicate desired timeline of the registration, especially if it must be completed promptly.
2. Documentation of current IRB approval must be on file with the DCC prior to registration of patients on this study for participating institutions.
3. The data manager/coordinator/research nurse should then e-mail copies to [[contact]](mailto:[contact]) of the following documents to the DCC:
  - Registration Cover Sheet (Appendix N)
  - Completed Eligibility Criteria List (printed from Section 3.1-2 of the protocol)
  - Source documentation to support eligibility criteria\*\*
  - Signed informed consent document
  - Signed HIPAA authorization form (if separate from the informed consent document)
  - Signed subject's Bill of Rights (COH only)

\*\*For COH participants, provide copies of source documentation only if not readily available as a finalized record in the COH EMR

4. After having received all transferred documentation, the DCC will complete the review the documents to verify eligibility, working with the COH staff and/or

participating institution as needed to resolve any missing required source elements. A subject failing to meet all protocol eligibility requirements will not be registered.

5. Once eligibility has been confirmed, DCC staff will register the participant by: assigning a subject accession number, register the subject on study centrally into MIDAS for all outside institutions (the COH CRC will directly accession into MIDAS), and enter the subject into the eCRF system, Medidata RAVE.
6. Once registration has been completed, DCC staff will send a Confirmation of Registration Form, including the participant study number and planned start date of treatment to:
  - o the participating institution's study team: site PI, treating physician, protocol nurse, CRC and pharmacy.
  - o the sponsor team: ([name], [name], COH CRN and COH CRC).

#### **6.4 Dose Assignment**

Study patients will receive the same initial dose of study agents (see **Section 7.0**). Dose reductions can occur if medically necessary as described below (see **Section 8**).

### **7.0 Study Treatment Protocol**

---

#### **7.1 Treatment Overview**

Treatment will be administered in an outpatient setting.

##### **7.1.1 Neratinib**

**7.2 Neratinib investigational product will be supplied as 40 mg film-coated tablets packaged in bottles with desiccant. Neratinib (240 mg initial dose; provided as six 40 mg tablets) will be self-administered orally by patients on a daily basis, starting with Cycle 1/Day 1. Neratinib must be taken with food, in the morning. Neratinib is to be taken continuously in 28-day cycles, with no rest between cycles. Doses missed for toxicity will not be made up. Dose Adjustment**

Management and dose modification associated with adverse events are outlined in **Section 8**.

#### **7.3 Planned Duration of Therapy**

The treatment will be continued until one of the following occurs:

- Progression of disease.
- Concurrent illness that prevents further administration of treatment.
- Unacceptable adverse event(s) as defined in Section 6 below.
- Patient decides to withdraw from the study.
- General or specific changes in the patient's condition render the patient unacceptable for further treatment in the judgment of the investigator.

#### **7.4 Criteria for Removal from Treatment**

- Adverse Events.

- Current illness that prevents further administration of treatment.
- General or specific changes in the patient's condition which render the patient unacceptable for further treatment in the judgment of the investigator.
- Clinical disease progression confirmed by imaging.
- Withdrawal of consent.

## 7.5 Subject Follow-Up

Throughout the study, reconciliation will be made between the amount of investigational product supplied, dispensed, returned, and subsequently destroyed or returned to IDS pharmacy. All investigational products that were supplied by the sponsor will be returned to IDS pharmacy, or destroyed at the site in accordance with COH guidelines. Individual patient dosing compliance should be reviewed at each study visit by study site staff. If patient non-compliance is noted, the patient should be re-instructed regarding proper dosing procedures in order to continue in the study. If repeated non-compliance is noted, additional steps may be taken, including withdrawal of the patient from the study. Subjects will be followed for toxicity outcomes for an additional 30 days after stopping the drug and until resolution of all grade  $>2$  toxicities. Patients removed from study for unacceptable adverse events will be followed until resolution or stabilization of the adverse event, even after disease progression is noted. All patients will be passively followed until death, though active follow-up will cease upon removal from study.

## 7.6 Supportive Care, Other Concomitant Therapy, Prohibited Medications

All concomitant treatments, therapies and medications will be captured from the signing of the ICF until the end of the treatment. This will include the start date, stop date, generic name, route of administration, dose and indication for treatment. At screening, patients will be asked what medications they have taken during the last 30 days, which medications are ongoing at the time of screening, any medical conditions that require medication, and all prior cancer therapies. At each subsequent study visit, patients will be asked what concomitant medications they are currently taking.

All concomitant medications taken during the study treatment will be recorded in the Case Report Form. The minimum requirements are drug name and dates of administration. All prescription and over-the-counter medications that have been taken within one month prior to the first dose of investigational treatment should also be reported in the Case Report Form. Patients should receive full supportive care during the study, including treatment with antibiotics, antiemetics, blood transfusions, antidiarrheals, and analgesics as appropriate, with the exception of drugs listed in **Section 7.6.3 and 7.6.4**.

### 7.6.1 Required Concomitant Treatment

#### 7.6.1.1 Loperamide Antidiarrheal Therapy

Diarrhea is the major dose-limiting toxicity of neratinib with onset typically occurring early in the course of treatment (during the first few weeks). Primary prophylactic use of antidiarrheal medication is **mandatory** for all enrolled patients in the neratinib study.

Loperamide is the recommended standard therapy to treat diarrhea in this study. If alternative antidiarrheal medication is proposed, this should be discussed with the PI and the reason documented in the source documents. Second-line antidiarrheal treatments and adjunctive

therapies (i.e., octreotide [SANDOSTATIN®]) (or equivalent as approved by the PI) are also recommended for use when appropriate.

All patients are required to receive intensive diarrhea prophylaxis:

- For the first 14 days, loperamide 4 mg (2 tablets/capsules) will be self-administered orally by patients 3 times a day (total 12 mg a day). The initial dose of loperamide 4 mg will be self-administered orally with the first dose of neratinib.
- After the first 14 days, loperamide 4 mg (2 tablets/capsules) will be self-administered orally twice a day (total 8 mg a day) through the first cycle of therapy (Day 28) from start of neratinib dosing.
- Thereafter, loperamide will be administered as needed (not to exceed 16 mg per day). The goal is to titrate to 1-2 bowel movements a day. Recommended loperamide dosing is listed below in **Table 5**.

**Table 5: Loperamide Dosing**

Day	Loperamide Dose
1	4mg at time of first dose of neratinib, then 12mg in 3 divided dose of 4mg tid
2-14	Daily dose of 12 mg in 3 divided doses of 4 mg tid
15-28	Daily dose of 8 mg in 2 divided doses of 4 mg bid
29+	Daily dose as needed (not to exceed 16 mg per day)

Patients must use a diary to record intake of loperamide. Loperamide pill counts will be conducted during the first 2 cycles (56 days) of therapy.

#### **Loperamide Dose Adjustment:**

Patients are expected to take loperamide prophylaxis as directed. However, patients may require individualization of loperamide prophylaxis dose (up to a maximum dose of 16mg per day) with the goal of titrating to 1-2 bowel movements a day.

- For patients who develop diarrhea during Cycles 1-2, loperamide should be increased up to a maximum of 16 mg a day.
- If a patient is unable to tolerate loperamide due to symptomatic constipation, loperamide should be held until after the first bowel movement and then resumed at a dose reduced by one level.
- For recurrent symptomatic constipation events, hold loperamide until after the first bowel movement and then resume at a dose reduced to the next lower dose level.
- If a patient is unable to tolerate once-daily loperamide due to constipation, hold loperamide and discuss subsequent loperamide dosing with the Medical Monitor.
- Neratinib dosing should continue if loperamide is held.

Recommended dose reductions for the -1 and -2 dose levels of loperamide are listed in **Table 6**.

**Table 6: Loperamide Dose Reduction Levels for Constipation**

Dose Level	Loperamide Dose	Tablets/Capsules per Day
0	4 mg TID	6 tablets/capsules a day
-1	4 mg BID	4 tablets/capsules a day
-2	2 mg TID	3 tablets/capsules a day
-3	2 mg BID	2 tablets/capsules a day
-4	2 mg once a day	1 tablet/capsule a day

Abbreviations: BID = twice daily; mg = milligrams; TID = three times daily

The Investigator/study nurse must review with the patient the **patient instructions (Appendix K)** for the management of diarrhea and the **Patient Diary (Appendix M)** for the patient's daily recording of investigational product during the first 2 cycles, number of stools, and use of loperamide and/or other anti-diarrheals. Both the patient and the Investigator/study nurse must sign the patient instructions for the management of diarrhea. The Patient Instructions and Patient Diary are to be handed to the patient before leaving the site with investigational product on or before Cycle 1/Day 1, with clear instructions to contact the Investigator in the event of *de novo* onset or persistent Grade  $\geq 2$  diarrhea to discuss the appropriate course of treatment.

An “Optimal Management of Diarrhea Checklist” (**Appendix L**) will be reviewed and signed by study investigator or study nurse on Cycle 1 Day 1. The study team will call patients at 1 day, 2 days and 3 days after first dose of neratinib to assess tolerance.

Documentation of any occurrences of stools or diarrhea must be as precise as possible and captured in the Patient Diary. For AE recording, documentation of “intermittent” events of diarrhea is limited to Grade 1. If events of Grade 1 diarrhea are separated by 3 days without any diarrhea, then each event must be documented as separate AEs with corresponding start and stop dates.

The entries on the Patient Diary should be reviewed together with the patient for the first 2 cycles. If the patient has experienced diarrhea since the last visit, details of the daily number of stools provided on the diary help to grade the diarrhea as precisely as possible (per NCI CTCAE v.4.0). Also, the daily dose of loperamide (or other anti-diarrheals, if applicable) noted on the diary for patients in the neratinib treatment will be reviewed and recorded on the CRF.

Loperamide will be dispensed directly by the site on or before Cycle 1/Day 1 with neratinib. It is very important to initiate treatment with loperamide concomitantly with the first dose of neratinib to minimize occurrence and severity of diarrhea.

#### 7.6.1.2 Prophylactic dosing instructions for Cycle 1

- Inform patients that they will experience diarrhea while taking neratinib.  
Administer loperamide:
  - For the first 14 days, loperamide 4 mg (2 tablets/capsules) will be self-administered orally by patients three times a day (total 12 mg a day). The initial dose of loperamide 4 mg will be self-administered orally with the first dose of neratinib.
  - After the first 14 days, loperamide 4 mg (2 tablets/capsules) will be self-administered orally twice a day (total 8 mg a day) through the first cycle of therapy (Day 28) from start of neratinib dosing.

- Thereafter, loperamide will be administered as needed (not to exceed 16 mg per day).
- The goal is to maintain the loperamide prophylaxis dose with a goal of titrating to 1-2 bowel movements a day.
- For patients who develop diarrhea during Cycles 1, loperamide should be increased up to a maximum of 16 mg a day.
- For patients with persistent Grade 1 diarrhea (<4 stools per day above baseline) on loperamide, Lomotil® (diphenoxylate hydrochloride and atropine sulfate) 1 tablet (2.5 mg) every 6 to 8 hours may be added (or equivalent as approved by PI).
- For Grade 2 diarrhea during Cycle 1 (4 to 6 stools per day above baseline, despite intensive loperamide): add lomotil 2.5mg every 6 to 8 hours, consider adding octreotide (short-acting) 150 µg subcutaneous [SC] injection 3 times a day, or after initial dose of short-acting octreotide, if well tolerated, a single dose of octreotide LAR 20 mg by intramuscular injection (equivalent medication may be used with approval of the Investigator). For persisting Grade 2 diarrhea during Cycle 1 despite the use of both imodium and lomotil: add octreotide as directed above.
- For Grade 3 diarrhea management during Cycle1: please refer to Table 7 and 8 for dose hold and reduction.
- For Grade 4 diarrhea management during Cycle 1: recommend permanently discontinue neratinib

The sites must contact the patient by phone at 1 day, 2 days, and 3 days after the first dose of neratinib:

- To inquire about any diarrhea and about potential AEs;
- To provide guidance to the patients for immediate and appropriate management of AEs, including diarrhea as specified in this protocol;
- To confirm that patient has loperamide available, in case needed;
- To inquire about the first date of neratinib intake; the Investigator/research staff must update the electronic CRF (eCRF) within 3 days of receipt of this information.

**(These phone calls are mandatory and must be recorded in the study chart together with response from the patient and action taken.)**

- Instruct patients to promptly report diarrhea symptoms.
- Instruct patient to record the number of stools per day and the dose of anti-diarrheal medication taken each for the first 2 cycles.

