## **8.0 Dose Delays/Modifications for Adverse Events**

---

Patients will be treated per protocol or until disease progression or withdrawal from treatment due to unacceptable adverse events or treatment consent withdrawal. At each study assessment, subjects are to be evaluated for evidence of drug-related adverse events.

In all cases where the subject is withdrawn due to unusual or unusually severe adverse event considered related to neratinib, the Investigator must report the withdrawal as a Serious Adverse Event.

Treatment may be delayed for up to 4 weeks, to allow for resolution of toxicity except in the event of those toxicities described below in which cases treatment must be discontinued permanently (see **Table 7**).

Recommended dose reductions for the -1 and -2 dose levels of Neratinib are listed as following:

Dose level	Neratinib
Starting dose	240mg
-1	160mg
-2	120mg

If a dose of neratinib is held, study procedures for that cycle will proceed on schedule as planned, without any delay. This also applies to tumor assessments, which should continue to be done every 12 weeks, starting from the first dose of neratinib until the first planned tumor assessment at 12 weeks ( $\pm 1$  wk), and then after every subsequent 12 weeks ( $\pm 1$  week) of treatment regardless of any changes in dose or occurrence of AEs. Missed dose(s) of neratinib (i.e., any

dose that is not administered within the protocol-defined administration window) will not be made up. The dose adjustment guidelines represent the minimum set of measures that investigators must follow. However, additional measures may be taken as necessary, for certain patients per the Investigator's medical judgment. All dose modifications/adjustments should be documented in the patient's source file.

Once neratinib dose has been reduced for a patient, all subsequent cycles must be administered at that dose, unless further dose reduction is required. Dose re-escalation is not permitted.

If a patient developed AE requiring dose reduction while on neratinib dose level of 120mg, neratinib will be discontinued.

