## 8.1 General Toxicities

Detailed guidelines for dose adjustments of neratinib for general toxicities (exclude alopecia) are shown in **Table 7**. Grade 2 or 3 toxicities that are unrelated to neratinib will be excluded from the dose adjustment.

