**Table 7: General Toxicities Requiring Dose Adjustment of Neratinib\***

NCI CTCAE v.4.0	Action
Grade 3 adverse reaction	
1st appearance	Hold neratinib until event resolves to Grade $\leq 1$ ; then resume neratinib at one dose level lower, lowest dose of neratinib is 120mg.
2nd appearance	Hold neratinib until event resolves to Grade $\leq 1$ ; then resume neratinib at one dose level lower, lowest dose of neratinib is 120 mg
3rd appearance	Discontinue neratinib permanently.
Grade 4 adverse reaction	

Any	Discontinue neratinib permanently.
-----	---

Based on NCI CTCAE v.4.0: National Cancer Institute Common Terminology Criteria for Adverse Events Version 4.0.

\* Grade 2 or 3 toxicities that are unrelated to neratinib will be excluded from the dose adjustment.

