**Table 8: Gastrointestinal Toxicities Requiring Dose Adjustment of Neratinib**

NCI CTCAE v.4.0	Actions
Grade 1 Diarrhea: Increase of $\leq 3$ stools per day over baseline. OR Grade 2 Diarrhea: Increase of 4-6 stools per day over baseline. Lasting <math>\leq 5</math> days	Adjust antidiarrheal treatment per the guidelines for management of diarrhea at the first onset of diarrhea (refer to Section 7.6.1.1 ). Instruct patient to follow dietetic recommendations in the guidelines for management of diarrhea. Fluid intake of $\sim 2$ L/day should be maintained to avoid dehydration.
Grade 3 Diarrhea: Increase of $\geq 7$ stools per day over baseline; incontinence; hospitalization indicated; limiting self-care and activities of daily living. Lasting <math>\leq 2</math> days	Adjust antidiarrheal treatment per the guidelines for management of diarrhea at the first onset of diarrhea (refer to Section 7.6.1.1 ). Hold neratinib until recovery to Grade $\leq 1$ or baseline. Instruct patient to follow dietetic recommendations of the guidelines for management of diarrhea. Fluid intake of $\sim 2$ L/day should be maintained by IV, if needed. If recovery occurs: 
 
<math>\leq 1</math> week after withholding treatment, resume neratinib at the next reduced dose level
 
Within 2-4 weeks after withholding treatment, reduce neratinib dose at the next lower dose.
 
 If event occurs a second time and the neratinib dose has not already been decreased, reduce neratinib dose to next lower dose level. If subsequent events occur, reduce the dose of neratinib to the next lower dose level. Once the event resolved to Grade $\leq 1$ or baseline, start loperamide 4 mg with each subsequent neratinib administration.

Grade 3 Diarrhea: lasting >2 days despite treatment with optimal medical therapy, or associated with fever, dehydration OR Any Grade 4 Diarrhea: Life-threatening consequences: urgent intervention indicated. (would recommend d/c)	Recommend permanently discontinue neratinib OR if Investigator deems it to be in the patient's best interest to continue, hold neratinib until AE resolved to Grade $\leq 1$ ; then resume neratinib at 120 mg.
--	--

Based on NCI CTCAE v.4.0: National Cancer Institute Common Terminology Criteria for Adverse Events Version 4.0.

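### Grade 4 diarrhea falls under two incompatible neratinib rules (Table 7 against Table 8), and the protocol does not say which table governs diarrhea

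*Combined protocol and SAP*

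**What the plan says.** **Grade 4, general rule.** Section 8.0 allows treatment to be delayed for up to four weeks, except for "those toxicities described below in which cases treatment must be discontinued permanently", and refers the reader to Table 7. Under the row heading "Grade 4 adverse reaction", Table 7 has a single line covering any such event. Its action is permanent discontinuation, with no investigator option. Section 8.1 sets the scope of that table: "Detailed guidelines for dose adjustments of neratinib for general toxicities (exclude alopecia) are shown in" Table 7. Besides alopecia, the only other exclusion is grade 2 or 3 events unrelated to neratinib.

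**Grade 4, diarrhea.** Table 8 puts any grade 4 diarrhea in the same row as grade 3 diarrhea that lasts more than two days or comes with fever or dehydration. The action is "Recommend permanently discontinue neratinib" or, "if Investigator deems it to be in the patient's best interest to continue, hold" until the event falls to grade 1 or below and then resume at 120 mg. Section 7.6.1.2, which covers Cycle 1, has "For Grade 4 diarrhea management during Cycle 1: recommend permanently discontinue neratinib" and cites no table.

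**Grade 3 in Cycle 1.** Section 7.6.1.2 says "For Grade 3 diarrhea management during Cycle1: please refer to Table 7 and 8 for dose hold and reduction". Section 8.2, on gastrointestinal toxicity, names Table 8 only.

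Section 8.0 also describes the dose-adjustment guidelines as a minimum that investigators must follow, and allows them to take further measures.

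**The concern.** A site treating a patient with grade 4 diarrhea can follow Table 8, resume neratinib, and thereby breach Table 7. Table 8 itself describes grade 4 diarrhea as life-threatening. The protocol calls diarrhea the drug's major dose-limiting toxicity and regards older adults as especially vulnerable to it. Whether the same act counts as permitted treatment or as a protocol deviation depends on the page that was read, and Section 16.4 allows further sites to enroll.

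The statistical consequence is smaller. Rates of dose reduction and holds are secondary results, reported with exact confidence limits (Section 15.3) and reviewed at the interim analysis (Section 15.2.1). Section 2.2 adds drug-related discontinuation. If sites apply different rules, these rates partly reflect the choice of table rather than the tolerability of the drug.

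**Working it through.** The check is mainly a comparison of text. The plan gives no figure of its own for this point.

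**Step 1. Trace each event through both tables, starting from 240 mg.**

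| Event | Table 7 | Table 8 | Compatible? |
|---|---|---|---|
| First grade 3 diarrhea, 2 days or less, uncomplicated | Hold, resume one level lower (160 mg) | Hold, resume one level lower (160 mg) | Yes, same path |
| First grade 3 diarrhea, over 2 days or with fever or dehydration | Hold, resume one level lower (160 mg) | Stop recommended, or hold and resume at 120 mg | Yes, if Table 7 is a minimum: both Table 8 actions are stricter |
| Any grade 4 diarrhea | Permanent stop, no option | Stop recommended, or hold and resume at 120 mg | No: Table 8 allows what Table 7 rules out |

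**Step 2. Look for a sentence that resolves the grade 4 row.**
- Section 8.1 does not take diarrhea out of Table 7.
- Section 8.2 points to Table 8 but does not say that it replaces Table 7.
- The minimum-measures sentence in Section 8.0 permits more than the guidelines require. It cannot turn a required stop into an optional one.
- Section 7.6.1.2 applies Table 7 to diarrhea, at grade 3, so the protocol does not treat Table 7 as irrelevant to diarrhea.
- Section 7.3 ends treatment for "Unacceptable adverse event(s) as defined in Section 6 below", but Section 6 covers screening and registration and contains no such definition.

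None of these settles it.

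**Step 3. Expected frequency of the grade 4 conflict.** Inputs: 3 grade 4 diarrhea events in 476 monotherapy patients (Table 1 and Section 10.2.1), and n = 40 (Section 15.1).
- Rate: 3/476 = 0.0063; exact 95% CI 0.0013 to 0.0183.
- Expected count: 40 × 0.0063 = 0.25 (0.05 to 0.73 across the interval).
- P(at least one) = 1 − (1 − 0.0063)^40 = 0.22 (0.05 to 0.52).

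Section 10.2.1 says these events occurred before the intensive diarrhea plan and that no grade 4 diarrhea was reported with loperamide prophylaxis, which this trial mandates. The true chance may therefore be lower.

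**Step 4. Reach of the grade 3 ambiguity.** With prophylaxis, Section 10.2.1 gives 12–16% grade 3 diarrhea: 40 × 0.12 = 4.8 and 40 × 0.16 = 6.4 patients. The tables differ only for the share q of episodes that are prolonged or complicated. The documents do not give q. Taking it as an assumption anywhere from 0 to 1, the expected number affected runs from 0 up to 4.8–6.4.

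**Step 5. Effect on reported rates.** One patient handled differently moves a rate by 1/40 = 2.5 percentage points. The primary endpoint counts a patient once a grade 2 or higher attributed toxicity occurs, and Table 17 counts a patient once grade 3 or higher diarrhea occurs in the first two cycles. Both are settled by the event itself, before the choice of table matters.

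**The case against.** The strongest reply is that the layout of Section 8 already answers the question. Table 7 is headed as general, and separate tables follow for gastrointestinal, lung, liver and LVEF toxicity. Those tables depart from Table 7 elsewhere: Table 9 stops neratinib at grade 3 pneumonitis, where Table 7 would hold and resume, and Table 10 stops at a recurrent grade 3 ALT or bilirubin after one reduction, where Table 7 waits for a third appearance. Table 8 is the only one of these tables to name grade 4 diarrhea. On this reading the organ-specific table governs, and only a precedence sentence is missing.

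That reading is plausible, but the protocol never states it. The departures in Tables 9 and 10 are stricter than Table 7 and so fit with Table 7 as a minimum; the grade 4 option in Table 8 is looser and does not. Section 7.6.1.2 also sends diarrhea to Table 7, which undercuts the idea that Table 8 stands alone.

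Three other parts of the reply stand:
- A reader might infer that Section 8.0 itself orders a stop for grade 4 diarrhea. It names neither grade 4 nor diarrhea; the mandatory rule comes from Table 7, to which Section 8.0 points.
- A reader might infer that the grade 3 rules contradict each other as well. For a prolonged or complicated first episode, following Table 8 also satisfies Table 7 as a minimum, so the gap is an unstated precedence.
- The conflict will rarely be met. Section 14.2.3 also lets the principal investigator clarify ambiguous points, although case by case and without removing the inconsistency from the text.

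**Conclusion.** The grade 4 conflict is real as written: Table 7 requires a permanent stop, while Table 8 and Section 7.6.1.2 only recommend one, and Table 8 allows resumption. For Cycle 1 grade 3 diarrhea the defect is narrower: two tables are cited and neither is given precedence.

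The size is modest. About 0.25 of 40 patients are expected to meet the grade 4 conflict, with a 22% chance of at least one (5% to 52% across the exact interval). This assumes that the pooled rate from before the intensive plan carries over to this trial, which may overstate it. The number touched by the grade 3 ambiguity cannot be fixed, because the documents do not give the share of prolonged or complicated episodes.

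What is affected is the safety of individual patients and the descriptive rates of dose modification and discontinuation. A reader might infer that the trial's main result is compromised, but the primary endpoint, the sample size and the Table 17 boundary do not depend on which table is followed.

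Two neighbouring slips are editorial only and add no weight: the pointer in Section 7.3, and the loperamide wording. On Day 1 the text gives 12 mg and Table 5 gives 4 + 12 = 16 mg, which is within the stated daily maximum. As-needed use starts after Day 28 in the protocol, but after two cycles in one Appendix K item.

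This is a clarification worth making because it concerns a life-threatening event and costs little. It does not threaten the validity of the trial.

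**What to change.** The clinical team should reconcile Section 7.6.1.2, Section 8.0, Table 7 and Table 8 so that grade 4 diarrhea has one rule. Matching wording would do this; so would a general rule with an expressly stated exception. Section 8 and Section 7.6.1.2 should also say which table governs diarrhea, which would settle the grade 3 reference too. No view is given here on which rule is right.

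The same amendment can correct the Section 7.3 cross-reference and bring the loperamide text, Table 5 and Appendix K into agreement.

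The cost is a text amendment and, if Appendix K changes, a reissued patient sheet. No visits, samples or data items are added, and the statistical analysis does not change.
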